D.8. Monitoring of Trial Conduct will be ongoing. D.8.a. Intervention Fidelity. Fidelity to CSNAT competency criteria will be accomplished during 3-day Protocol Training and monitoring by [name] in consultation with [name]. [name] and [name] will review all recordings of Session 3, Respecting Choices conversation to ensure intervention fidelity. D.8.b. Procedure Monitoring. [name] and [name] will monitor ongoing IRB compliance, documentation and preparation for annual continuing reviews. [name] and/or [name] will assure standardization of procedures, resolve any problems that are identified, confirm that all consents have occurred properly, and maintain participant and regulatory data D.8.c. Data quality monitoring. The REDCap database from previous FACE studies has been updated and expanded for this study. The system in place for data entry and implementation will be updated. See Resources for details. D.8.d. Safety Monitoring Committee (SMC) will meet twice yearly or more often as needed. See Data Safety and Monitoring Plan. The external SMC will be assembled by [name] and have the responsibility of reviewing safety information, study progress, and other relevant data. Duties will include review of any serious adverse event (SAE) or adverse event (AE), recommending follow-up or further action to the PI.

D.9. Analytic Plan. Various statistical methods, such as descriptive statistics, paired t-test, reliable change index (RCI), Fisher's exact test, and generalized estimating equation (GEE) models will be used to evaluate the proposed aims. All models will be estimated Bayesian approach. As such, data non-normality due to the small sample size can be handled in modeling under the assumption of missing at random (MAR). MAR is a plausible assumption that allows missingness to be dependent on observed measures (e.g., individual characteristics, intervention assignment, and/or baseline outcome measures).

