16	Satisfaction Questionnaire	5	It was too much to handle	Agree/Strongly Agree
16	Satisfaction Questionnaire	7	It was harmful	Agree/Strongly Agree
Form	Name	Item	Question	Answer
16	Satisfaction Questionnaire	1	It was useful	Disagree/Strongly Disagree
16	Satisfaction Questionnaire	2	It was helpful	Disagree/Strongly Disagree
16	Satisfaction Questionnaire	6	I felt satisfied	Disagree/Strongly Disagree
16	Satisfaction Questionnaire	11	I felt courageous	Disagree/Strongly Disagree
16	Satisfaction Questionnaire	13	It was worthwhile	Disagree/Strongly Disagree

For the purposes of this study an adverse event is when ONE of the following statements are endorsed on the . **Agree or strongly agree:**

- o "It was too much to handle." OR
- "It was harmful."
 AND

In addition to one of the above statements being endorsed, ALL of the following must be endorsed for an adverse event to occur. **Disagree or Strongly Disagree**

- "It was useful."
- "It was helpful."
- o "I felt satisfied."
- "I felt courageous
- "It was worthwhile."

Definition of Serious Adverse Events (SAEs)

For the purposes of this study a serious adverse event will be defined as an emotional breakdown requiring hospitalization or inpatient behavioral health services for emotional distress very likely/certainly related to the study intervention.

Any serious adverse event occurring during the protocol conduct will be reported and reviewed by the PI, [name]. Any serious adverse event will be monitored to ensure the event was actually caused by the intervention, and not some coincidental issue. These events will be collected and reported in compliance with the local IRB guidelines. The PI and *IRB* must be notified within 24 hours of the reported serious adverse event. We will discontinue the study until a corrective action plan is in place.

The PI and *IRB* must be notified not more than 5 days after becoming aware of an adverse event. Training will continue throughout the course of the study to minimize the likelihood of such an SAE.

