supportive, caring and respectful way, some participants may become aware of painful feelings of guilt, anger or sadness. If a family member is overwhelmed by strong feelings, the RA, who is clinically experienced and trained in active listening and affect regulation, will provide support. After support is provided the RA will ask if the family would like to continue, take a break, or reschedule for another day. We will not remind the family at this time that they can discontinue the study, as they may experience this as abandonment or punishment for expressing strong feelings. However, participants will have been told during enrollment that they may withdraw from the study at any time and will be reminded of this when confirming the next scheduled appointment.

If the family member continues to be distressed, the RA will ask if there is a staff person they feel really good about that they would like to meet with and we will contact that staff person to support the participant. If yes, the RA will stay with the family until the staff person arrives or accompany the family to the staff person's office and wait with the participant until the participant is seen.

If the family member expresses suicidal, homicidal or psychotic thoughts during the course of the intervention the procedures for managing this event will be followed as described in "1. *Screening*" from list above.

4. Assessment at 3 months post-intervention. The same procedures will be followed as described during the screening process.

To further protect against risks, we will continue with the following protections, which we put in place for our previous pediatric advance care planning studies:

- 1) We will hire staff with experience, maturity, good basic communication skills and good interpersonal skills;
- 2) RAs hired to be Interventionists who do not meet certification criteria for the RC Interview will not be allowed to interact with participants;
- 3) We will provide ongoing intensive and comprehensive training. For example, in addition to what was described earlier, Respecting Choices Facilitators participate in two days of multiple role plays of possible adverse events that could occur during the Respecting Choices Interview. Scenarios will be given which were known to have ever come to the attention of the ethics board at Children's National, so that we will be as prepared as possible for any eventuality;

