As with our previous studies, we will send study results for primary outcomes to study participants in the form of a newsletter. For those patients who may die while on study, the newsletter will be accompanied by a personal letter expressing sorrow for the loss of their child and appreciation for their participation and contribution to the science of pACP. This letter will be personalized and signed by the research staff known to the patient and family.

The risks of participation in this minimal risk study are reasonable in relation to the importance of the knowledge that may result from the study.

Study participants who were randomized to the control condition will be offered the intervention while the study is in the dissemination stage, if study aims are realized. The Co-ls at Children's National are committed to this, as a study service.

Safety Monitoring Committee (SMC)

This study will be conducted in accordance with appropriate sections of the International Conference on Harmonization's Guidelines for Good Clinical Practice (GCP). The principal investigator, [name], will be responsible for monitoring and the process by which adverse events and unanticipated problems will be reported to all relevant regulatory bodies. See **Data Safety and Monitoring Plan** for more details.

[name] will compile a Safety Monitoring Committee (SMC), following the guidelines provided by NINR/NIH. [name] will invite an expert in the full range of issues associated with children with serious illnesses and their families, with additional expertise in evidence-based assessment and intervention, specific to the goals of this Program Announcement to identify and meet the palliative care needs of persons with rare diseases and their families. Three additional members will be invited who are experts on quality of life measurement, data safety, and the science and ethics of research on palliative care for children.

The SMC will meet a minimum of once a year. The SMC will decide what data summaries it wants to see in order to adequately monitor the data and the safety of the patients and families in the study.

The SMC will review all adverse events, for immediate assessment of any safety concerns in the study. All serious adverse events will be reported to the PI, SMC and the IRB within 24 hours of event knowledge. [name] will then notify the Research Nurse Coordinator, [name], who will coordinate notifications.

References

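### A caregiver emergency activation after randomization that ends without intervention-related inpatient care can leave the AE and SAE counts at zero, and the protocol text neither counts it nor sets an IRB or SMC notice time for it

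*Combined protocol and SAP*

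**What the plan says.** All references are to the combined protocol and SAP.

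- **Emergency procedures.** Under Families in emotional distress, item 1 (Screening), current suicidality, homicidality or active psychosis sets off a chain: the research assistant contacts the PI, failing that an on-call clinician, failing that the emergency department. Item 3 carries this into the sessions: "If the family member expresses suicidal, homicidal or psychotic thoughts during the course of the intervention the procedures for managing this event" are those of item 1. Item 4 applies them at the 3-month assessment. Item 6 of the later list of protections covers the sessions and any assessment.
- **AE.** "For the purposes of this study an adverse event is when ONE of the following statements are endorsed on the" Satisfaction Questionnaire: too much to handle, or harmful. All five positive items must also be rejected. None of the seven items concerns suicidal, homicidal or psychotic thoughts.
- **SAE.** "a serious adverse event will be defined as an emotional breakdown requiring hospitalization or inpatient behavioral health services for emotional distress", and the distress must be judged very likely or certainly related to the intervention.
- **Notice times.** The PI and IRB "must be notified not more than 5 days after becoming aware of an adverse event". For SAEs, "All serious adverse events will be reported to the PI, SMC and the IRB within 24 hours of event knowledge". The REDCap alert fires on the questionnaire criteria.
- **SMC.** D.8.d gives it a general remit to "have the responsibility of reviewing safety information, study progress, and other relevant data" and says it "will meet twice yearly or more often as needed". The later Safety Monitoring Committee section says "The SMC will meet a minimum of once a year", lets the committee choose its data summaries, and mentions reporting of unanticipated problems without defining them or giving a time. Both sections refer to a Data Safety and Monitoring Plan that is not in the document.
- **Analysis.** D.9 covers quality of life, satisfaction, advance care planning documents and healthcare utilization. It has no summary of AEs, SAEs or activations.

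**The concern.** Emotional distress or family conflict is the first risk the protocol lists, and it treats these thoughts as needing an immediate assessment of danger. Yet the safety categories that carry a notice time rest on two other things: how the caregiver rated the experience on a questionnaire, and whether related inpatient care followed. The event that the protocol handles most urgently can therefore fall outside both.

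What is at stake is the meaning of a zero. The section on adverse events and the one on the intervention both cite the absence of such events in earlier trials as reassurance, and this pilot is meant to lead to a larger trial. A count of no AEs and no SAEs would naturally be read as evidence that the sessions are emotionally safe. As defined, that count is compatible with one or more emergency activations.

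**Working it through.** The plan states no figure to reproduce; the check is mainly one of logic.

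**1. Which activations are recorded as an event?** Three yes/no facts matter: inpatient care (I), judged related to the intervention (R), and the questionnaire pattern (Q). By the definitions, SAE = I and R; AE = Q.

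| I | R | Q | Recorded as |
|---|---|---|---|
| no | no | no | nothing |
| no | no | yes | AE |
| no | yes | no | nothing |
| no | yes | yes | AE |
| yes | no | no | nothing |
| yes | no | yes | AE |
| yes | yes | no | SAE |
| yes | yes | yes | SAE and AE |

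Three of the eight rows give neither, including one in which the distress is related to the intervention. Without related inpatient care, only Q produces a record.

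**2. How narrow is Q?** With each of the seven items reduced to agree or disagree there are 2^7 = 128 patterns. Q needs at least one of two negative items endorsed (3 ways) and all five positive items rejected (1 way): 3 × 1 = 3 of 128. This describes how specific the rule is; it is not a probability.

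**3. Can Q coincide in time?** Table 2 puts the Satisfaction Questionnaire at Visit 4, and D.6 puts brief satisfaction assessments at Visits 2, 3 and 4. Neither lists it at 3 months, which Table 2 labels separately. For FACE-Rare caregivers an activation at 3 months therefore has no questionnaire scheduled alongside it. For controls the timing is unclear: H2 compares their satisfaction, D.3 schedules them only for assessments, and the visit figure is not shown.

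**4. How likely is an activation?** The protocol gives no rate, so these risks are assumptions for illustration. P(at least one) = 1 − (1 − p)^n.

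| Assumed p | n = 15 (FACE-Rare) | n = 30 (both arms) |
|---|---|---|
| 1% | 14% | 26% |
| 2% | 26% | 45% |
| 5% | 54% | 79% |
| 10% | 79% | 96% |

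**5. What would the count say?** Exact (Clopper-Pearson) two-sided 95% upper limits; for zero events, 1 − 0.025^(1/n).

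- n = 15: 0 events 21.8%, 1 event 31.9%, 2 events 40.5%.
- The 3-month visit has two stated sizes: 25–26 dyads (Power & Sample Size Consideration; 30 × 0.85 = 25.5), or 12–13 per arm, and 21 dyads (Human Subjects Involvement), or 10–11 per arm. Across 10–13 per arm the limit is 24.7% to 30.8% for 0 events and 36.0% to 44.5% for 1.

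None of these results would establish safety. The point is that one or two real activations could be reported as zero.

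**The case against.** The strongest reply is that these events are not lost, and much of it stands. The PI or an on-call clinician is involved at once. Weekly meetings with the PI discuss issues from the sessions, and Session 3 recordings, where consented, are reviewed partly for safety. The SMC shares responsibility for the procedures being followed and documented in process notes, has a general safety remit, and can meet as needed. Unanticipated problems are a further reportable class. The definitions were approved for earlier studies by the IRB, which had thought the bar for an AE too low. Caregivers with active suicidality, homicidality or psychosis are not enrolled, which favours the lower assumed rates. The missing monitoring plan may already set a notice time.

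This answers the stronger readings that a reader might infer:

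- *That such events would go unmanaged or unseen.* The routes above say otherwise.
- *That the SMC would wait 6 or 12 months.* That assumes no route other than scheduled meetings is used, and D.8.d allows extra ones.
- *That the questionnaire can never coincide at 3 months.* Its timing for controls is not clear enough to say so.
- *That the zero counts in earlier trials are wrong.* Nothing in the document bears on that.

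It does not answer the narrower point. Process notes carry no count or deadline, unanticipated problems have neither definition nor time, and the timed notices attach to AEs and SAEs.

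**Conclusion.** The point holds as a gap in counting and timed notice, not in clinical care. A post-randomization activation without intervention-related inpatient care is neither an AE nor an SAE unless the questionnaire pattern coincides. The protocol text does not count it or set an IRB or SMC notice time, and D.9 would not report it. A published zero could therefore follow a real emergency activation.

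The logic needs no assumption beyond the definitions as written. The size does: the 14% to 79% range rests on assumed risks of 1% to 10% in 15 caregivers, with independent events. The conclusion is conditional on the Data Safety and Monitoring Plan not already covering activations. Confidence is medium for that reason. The change should be made, but no efficacy estimate or test is affected.

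**What to change.** 1. **Leave the AE and SAE thresholds as they are.** State that any post-randomization activation of the screening procedures, in either arm and whatever its outcome or judged cause, is recorded as a separate category, or name it as an unanticipated problem in the Safety Monitoring Committee section.
2. **Set a notice time.** Notify the IRB within the existing 5-day AE time, and extend that time to the SMC. The extension is new, since the 5-day rule now names only the PI and IRB. Attach no automatic halt, unlike the SAE rule. If the Data Safety and Monitoring Plan already requires this, cross-reference it instead.
3. **Protect blinding.** The PI or an unblinded coordinator enters each activation, with its date, in one REDCap field restricted by study role, because an in-session entry reveals the arm. The blinded Assessor reports events found at 3 months to the PI and does not use the field.
4. **Add to D.9** a descriptive table by arm: caregivers with at least one activation, exact 95% limits, no test. Separate in-session events, which can arise only in FACE-Rare, from 3-month-visit events. Compare the latter between arms only if the screening questions are asked of both arms at that visit, and say so in the protocol.

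The cost is some wording, one field and one table. No visit or instrument is added if the screening questions are already repeated at 3 months. The downside is a few more notices and a possibly non-zero count.

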assent, the RA will conduct further screening for inclusion/exclusion criteria. *Baseline Visit:* At enrollment and prior to randomization, baseline measures in Table 3 will be obtained. Attendance will be recorded to assess effects of full vs. partial participation in FACE-Rare. *Follow-up Visit:* Blinded Assessor will obtain follow-up measures from families at 3-months post- intervention in person (clinic or home visit), by telephone or Telemedicine. See **Resources on Telemedicine**. **D.6.b. Measures**. Measures (**Table 2**) will be administered to the family by the blinded RA-Assessor. Investigators selected well-established measures with good reliability, validity, and normative data to increase replicability. Chart abstraction will be conducted by the blinded Assessor. A second blinded researcher will provide a validity *and* reliability check. Interrater reliability testing will be conducted. Rate differences will be reconciled by consensus, following well established procedures. ^{14,145} Disagreements will be resolved by the PI. See **Project Narrative** for questionnaire details.

Table 2: Measures	Method	Time	Description	
Primary Outcomes: *BL=Base	line *mo=mo	nth		
Beck Anxiety Inventory ¹⁴³	Survey	BL, 3 mo	QoL: emotional health. 21 items. Total Score will be used in analysis.	
FACIT-Spirituality-EX-Vs-4) ¹⁴⁴	Survey	BL, 3 mo	QoL : spiritual (meaning/purpose, peace). Is culturally sensitive to those with non-theistic beliefs. 23-items. Total Score will be used in analysis.	
Advance Care Document for Children with Rare Diseases ⁸⁴	Survey	3 mo	ACP Documentation in EHR & Decisional preferences- to continue all treatments; to continue all treatments with exceptions noted; to stop all treatments but comfort care.	
Standardized Data Abstraction Operationally defined ^{14,45,145} ,146	Chart Abstract	BL,3 mo or close-out	care prior to death, hospitalizations, Emergency Department visits, intensive care unit use,	
Moderators:				
Brief-Multidimensional Measure of Religion and Spirituality ^{62,63}	Survey	BL, 3 mo	Religious Coping : 5 items from our previous research: attend religious services, feel God's presence, pray privately, identify as religious, identify as spiritutal. 12,57,58	
Family Appraisal of Caregiving Questionnaire ¹⁴⁷	Survey	BL, 3 mo	Caregiver appraisal: caregiver strain, positive caregiving appraisals, caregiver distress, family well-being in past two weeks. 25 items.	
Time-Invariant Covariates:	•			

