H1b. Family caregiving appraisals will moderate effect of FACE-Rare on QoL outcomes. The interaction between a caregiving appraisal variable and intervention will be included in the GEE model described above to examine whether and how the intervention effect on QoL measures would be moderated by the family caregiving appraisal. If the interaction is statistically significant, we would conclude the intervention effect on the outcome depends upon the value of the caregiving appraisal. A positive coefficient (e.g., 0.2) of the interaction indicates that intervention effect would increase the magnitude of this coefficient (e.g., 0.2), corresponding to one unit increase in the caregiving appraisal score. Each appraisal measure will be recoded as the deviation from its grand mean so that the recoded appraisal measure has a meaningful 0 that represents the mean level of the appraisal in the sample. As such, the main effect of intervention is interpreted as the intervention effect corresponding to the mean level of the original appraisal measure (i.e., the 0 of the recoded appraisal measure). When the interaction effect is statistically significant, the corresponding main effect, no matter it is statistically significant or not, must remain in the model and be included in calculation of intervention effect.

Testing H1c. Religiousness will moderate the effect of FACE Rare on QoL outcomes. The same analytical approaches proposed for testing H1b will be applied to test **H1c**.

AIM 2. To evaluate the effect of FACE-Rare on satisfaction with study participation.

H2: FACE-Rare families will report significantly greater satisfaction, compared to controls. The same analytical approaches proposed for testing **H1a** will be applied to test **H2**.

AIM 3. To evaluate the initial efficacy of FACE-Rare on secondary outcomes: plans and actions: completion of and documentation of advance care plans in the electronic health record at 3-months post-intervention.

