- 4) The PI will meet weekly with Children's National researchers to provide support to the research team and to address any emotional reactions or concerns they (RAs) have about a new family under consideration for recruitment and enrollment or issues that arose in the course of an intervention session;
- 5) We have a chaplain and an ethicist available for referral to discuss spiritual struggles or to help process conflicts about treatment preferences:
- 6) Procedures are clearly delineated about what the RAs should do if a participant should become suicidal or homicidal or psychotic during the intervention sessions or during any of the assessments; and
- 7) The Pl's available by cell phone. All research participants have a copy of the assent/consent form, which will contain appropriate Investigator phone numbers.

In addition to the procedures already in place, if they should prove to be insufficient, we also have an additional Co-I at Children's National, [name], who is an expert in safety issues in conducting research with dying children. [name] and [name] share an office suite at Children's National and have easy access to one another for consultations. [name], Co-Is and the Safety Monitoring Committee, as well as the study staff, will be responsible for ensuring that these procedures are followed and documented in the process notes and that the safety of participants is protected.

Although this study will be examining spirituality/religious experiences and beliefs, the FACE-Rare study is not a religious or spiritual intervention. We are including everyone regardless of religious affiliation. Instructions for responding to assessment measures include a statement that "Not all of these questions may apply to you. Please answer as best you can." Data on religious affiliation or no religious affiliation will be collected. If a participant gives no response, because it does not apply to him/her, the data will be coded as missing data.

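### Does recording not-applicable answers as missing undermine the test of religiousness as a moderator (H1c)?

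*Combined protocol and SAP*

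**What the plan says.** The coding rule is in Protection Against Risks, in the paragraph on spirituality and religious beliefs. That paragraph first gives the instruction printed with the assessment measures: "Not all of these questions may apply to you. Please answer as best you can". Next comes "Data on religious affiliation or no religious affiliation will be collected", and then the rule itself: "If a participant gives no response, because it does not apply to him/her, the data will be coded as missing data".

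Table 2 (D.6.b) lists five items for the religiousness moderator: attendance at services, feeling God's presence, and "pray privately, identify as religious, identify as spiritutal". The FACIT-Spirituality outcome is described there with the words "Is culturally sensitive to those with non-theistic beliefs".

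For H1c (labelled H2c in the Specific Aims), D.9 says "The same analytical approaches proposed for testing H1b will be applied to test" it, meaning a moderator-by-intervention interaction with the moderator centred at its grand mean. On missing data, D.9 states that "MAR is a plausible assumption that allows missingness to be dependent on observed measures", with "individual characteristics, intervention assignment, and/or baseline outcome measures" as examples. The documents supplied name no separate code for not applicable, skipped and refused. They also give no scoring rule for a partly answered five-item set.

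**The concern.** A non-religious caregiver might regard praying or feeling God's presence as not applicable and leave the item blank. The blank would then depend on the value that was not observed, and MAR given observed measures need not hold. Caregivers may also pass on or decline any question, so without a reason code three kinds of blank look alike, and the reason cannot be recovered later.

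H1c would suffer in one of two ways. If these caregivers are dropped, the moderator's range is cut at its lower end and the interaction is estimated less precisely. If their score is imputed under MAR, they are placed too high on religiousness and the slope is biased. Religiousness is a stated interest of this programme: the Significance section reports that it moderated an earlier effect of the intervention.

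**Working it through.** **Scope of the rule.** The sentence directly before it concerns affiliation, and the rule refers to a single thing that does not apply. On that reading H1c is untouched. The sentence before that concerns the assessment measures in general, which supports the wider reading. The text does not decide between them. A caregiver who answers no or never is unaffected under either reading.

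**Sample size.** 30 × (1 − 0.15) = 25.5, which reproduces the 25-26 dyads in Power & Sample Size Consideration. The documents give no blank rate, so 5% and 10% are assumed: 0.05 × 25.5 = 1.3 and 0.10 × 25.5 = 2.6 caregivers.

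**Upper bound on lost precision, without measurement error.** If the lowest fraction q of a normal moderator is lost altogether, the standard error grows by 1/√[(1 − q) × V], where V is the variance of the normal distribution left after truncation.
- q = 5%: V = 0.810, and 1/√(0.95 × 0.810) = 1.14.
- q = 10%: V = 0.712, and 1/√(0.90 × 0.712) = 1.25.

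**Simulation at n = 26** (20,000 runs). Assumptions: five four-category items with loading 0.8, a true interaction of 0.50 per SD, and a sharp cut-off so that exactly the least religious are affected. With complete data the slope is 0.45-0.46 (0.50 attenuated by item error), its SD is 0.44 and power is 17-18%. Each setting was simulated separately, so the complete-data slope varies slightly.

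| Handling of the affected caregivers | Result at 5% / 10% affected |
|---|---|
| 1-3 items blank, answered items averaged | SD 0.442 / 0.451 (×1.00 / ×1.02); slope unchanged |
| 1-3 items blank, caregiver dropped | SD 0.475 / 0.521 (×1.08 / ×1.18); slope 0.462 to 0.433 / 0.450 to 0.408; power 14% / 12% |
| All five blank, caregiver dropped | SD ×1.07 / ×1.17 |
| Whole score imputed under MAR, no auxiliary variable (n = 100,000) | 0.50 estimated as 0.548 / 0.558 |
| The same, with affiliation (assumed correlation 0.65) | 0.531 / 0.540 |

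The MAR bias is 0.548 − 0.50 = 0.048 and 0.558 − 0.50 = 0.058. Divided by 0.44 these are 0.11 and 0.13 of the SD of the estimate. The Monte Carlo error of each MAR estimate is about 0.01.

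**Effect on the H1c conclusion.** The conclusion under lowest-category scoring differs from the one with the item left missing in 0.3% / 1.3% of trials if answered items are averaged, and in about 7% / 10-11% if the caregiver is dropped.

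**What lowest-category scoring would do.** If all five items are blank because religiousness is low, it works well: slope 0.454 / 0.446 against 0.455 / 0.454 with complete data. If the blanks are unrelated to religiousness, it gives 0.409 / 0.356 against 0.467 / 0.455, a loss of 0.058 / 0.099. That exceeds the MAR bias of 0.048 / 0.058 which it would remove.

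**The case for a change.** The best case for acting is that the reason for a blank is cheap to record when the question is asked and cannot be rebuilt afterwards. Questionnaires are read to all caregivers, so one extra response code would do.

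The stakes also grow if blanks are common and lead to exclusion. With 20% or 30% of the least religious dropped, the standard error of the interaction rises by 1.47 or 1.70. For an assumed interaction of 0.8, power falls from 43% to 21% or 17%, against 34% or 28% for random skips. Grand-mean centring would then refer to a more religious subset: with a main effect of 0.50, the reported effect moves to 0.50 + 0.8 × 0.35 = 0.78 or 0.50 + 0.8 × 0.50 = 0.90.

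The point about recording the reason stands as good practice. The larger figures do not carry over. They need blank rates for which the documents give no support, and exclusion of the caregiver, which no section prescribes; D.9 points to modelling under MAR. The instruction to answer as best one can works against blanks. Recording an answer as missing does not rule out a reason code, and the Project Narrative and manual of operating procedures, where such detail may sit, are not among the documents supplied. Affiliation is collected and could count as an individual characteristic in the missing-data model, though the plan does not say that it will be used.

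**Conclusion.** No change to the plan is called for. What remains is a gap in written detail: which items the rule covers, and how a partly answered five-item set is scored. An analyst can settle both, and averaging the answered items leaves the slope unchanged and precision almost unchanged. Under the MAR modelling that D.9 adopts, the bias is about 0.1 of the SD of the estimate, and only when the whole score is missing. H1c is a secondary moderator question with about 17% simulated power on complete data, and the power section itself concedes weak power. The effect size that D.9 seeks for the later trial is the intervention mean difference, not this interaction. Scoring not-applicable answers at the lowest category is a trade-off with no clear gain, and at most an optional sensitivity run.

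This rests on assumed blank rates of 5-10%, a sharp cut-off, and assumed loadings, correlations and effect sizes. A much higher rate of fully blank sets, combined with exclusion of those caregivers, would matter more, but nothing in the documents points to either.
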